#### 2.3 Potential Risks and Benefits

As summarized above, GKT137831 has been extensively investigated in pre-clinical studies as well as in four studies in healthy volunteers and one study in subjects with Type 2 diabetes. GKT137831

Protocol No.: GSN000300	Compound No.: GKT137831
Protocol Version No.: Final 4.0; Amendment 3	Sponsor: Genkyotex
Protocol Date: 24 July 2018	Author: Cmed Clinical Services

was well tolerated when administered for up to 12 weeks at a dose of up to 200 mg BID. No safety signal or dose-limiting toxicities were identified in these studies. In particular, safety signals identified in toxicology studies were not detected. Specifically, there was no detectable drug effect on thyroid function, bone marrow function, liver function tests, or cardiac conduction. The careful extension of the treatment duration (i.e. 24 weeks) and dose increase to 400 mg BID are supported by the favorable safety data obtained in previous clinical studies. As a general precaution, however, appropriate safety endpoints have been built into this study for frequent monitoring (see Section 3). In addition, a SMB will carefully review the emerging study data on a regular basis in order to detect any safety signals early and take appropriate action according to the SMB charter.

Nevertheless, specific risks related to the subject population exist. GKT137831 caused minor elevations of total bilirubin in dog toxicology studies. These changes were transient and reversible, and were not associated with biochemical or pathological evidence of hepatocellular injury. The underlying cause for these changes has not been identified, and may involve competition for, or inhibition of, UGT enzymes which are responsible for the glucuronide conjugation. In phase 1 and phase 2 trials, GKT137831 did not cause elevations in total bilirubin. Nevertheless, this study will evaluate a higher dose over a longer treatment period, and drug accumulation in liver tissue is anticipated in PBC patients. Accordingly, the incidence of drug-induced liver injury (DILI) will be carefully monitored as outlined in Section 6.3.1.

In addition, a case of non-regenerative anemia was observed in the 26 week dog toxicology study. Accordingly, hematological parameters were carefully monitored in subsequent phase 1 and phase 2 studies. No safety signal related hematological parameters were detected in these trials. Nevertheless, hematological parameters will be carefully monitored as described in Section 6.3.2.

While NOX1/4 inhibition represents an attractive therapeutic strategy in patients with PBC, actual therapeutic benefits in PBC patients remain to be demonstrated.

## **3** OBJECTIVES AND ENDPOINTS

OBJECTIVE	ENDPOINT (OUTCOME MEASURE)
To evaluate the efficacy of oral GKT137831 in comparison with placebo, in subjects with PBC receiving UDCA and with persistently elevated serum ALP.	Primary efficacy endpoint:
	
 
The percent change from baseline to Week 24 (Visit 7) in serum GGT.
 

	Secondary efficacy endpoints:
	• Absolute and percent change in serum GGT from baseline to each assessment.
	• Absolute change in ELF score from baseline to Weeks 12 and 24.
	• Absolute and percent change in serum ALP from baseline to each assessment.
	• Absolute and percent change in serum levels of hsCRP, and fibrinogen, from baseline to each assessment.
	• Absolute and percent change in serum ALT, AST, conjugated and total bilirubin, from baseline to each assessment.
	• Absolute and percent change in the FIB-4 and APRI scores, from baseline to each assessment (FIB-4: age (years) x AST (IU/L)/(platelet count (10  /L) x (ALT (IU/L)  , APRI: AST (IU/L)/ upper normal limit AST)x100/platelet count (10  /L).
	• Absolute and percent change in liver stiffness as assessed by transient elastography (FibroScan ® or similar technology), from baseline to Week 24, in subjects with values at baseline and Week 24.
	• Absolute and percent change in serum levels of collagen fragments indicative of collagen formation and degradation, from baseline to Weeks 12 and 24.
	Absolute and percent change in Quality of Life (QoL), Fatigue and Pruritus scores based on the PBC-40 and Pruritus Visual Analogue Score (VAS), from baseline to Weeks 12 and 24.

.

	Tertiary efficacy endpoints:
	• Absolute and percent change in total bile acid levels from baseline to Week 12 and 24.
	• Proportion of subjects achieving a 15, 20, 30 and 40% reduction in serum ALP from baseline to each assessment.
	• Proportion of subjects who meet the definition of PBC responder criteria applying the Paris I, Toronto I, Toronto II, Toronto III, Toronto IV, Mayo II, and Barcelona disease prognostic risk criteria at Weeks 12 and 24.
	Exploratory Endpoints:
	• Optionally, absolute and percent change in serum C4 and FGF19 from baseline to Weeks 12 and 24.
	• Optionally, absolute and percent change in serum interleukin (IL)-6 and cytokeratin-18 (CK-18), from baseline to Weeks 12 and 24.
	
 
Optionally, absolute and percent change in serum IgM, IL-4, IL- 12, IL-17A, and interferon γ, from baseline to Weeks 12 and 24.
 

	Optionally, assessment of metabolomics signatures.
	Optionally, assessment of additional biomarkers of interest.
SECONDARY OBJECTIVES:	• Subjects with AEs from starting IMP to 28 days after the last administration.
To evaluate the safety of oral GKT137831 in comparison with placebo, in subjects with PBC.	• Clinical laboratory evaluations at Screening, baseline/Day 1 and Weeks 2, 6, 12, 18, 24 and 28.
	• Urinalysis at Screening and Weeks 12, 24 and 28.
	• Thyroid stimulating hormone (TSH) measured at baseline/Day 1 and Weeks 12 and 24.
	• Pulse rate, SBP and DBP at Screening, baseline/Day 1 and Weeks 2, 6, 12, 18, 24 and 28.
	Body weight at baseline/Day 1 and at Week 24.
	• 12-lead ECG during Screening and at Weeks 2, 12, and 24.
To estimate the population pharmacokinetics (PK) of GKT137831 and explore any potential PK-PD relationships	• Plasma concentrations of GKT137831 and its main phase 1 metabolite, GKT138184.
	The plasma concentrations will be subjected to population PK analysis to estimate population PK parameters such as clearance and volume of distribution and associated inter-individual variability

Protocol No.: GSN000300	Compound No.: GKT137831
Protocol Version No.: Final 4.0; Amendment 3	Sponsor: Genkyotex
Protocol Date: 24 July 2018	Author: Cmed Clinical Services

in this subject population.	(IIV), and to determine predictors of IIV.
	PK-PD analysis will be carried out using the primary endpoint and selected secondary endpoints in order to explore any potential PK-PD relationships. Exploratory Endpoint:
	• Additional biomarkers of interest will be measured in plasma or serum. The identity of these exploratory markers will be defined in response to findings described in the literature or obtained in this study. These markers will not have diagnostic or prognostic value and will not have an established normal range according to the World Health Organization (WHO).
To explore any relationship between genetic parameters and therapeutic responses in a subset of subjects.	• Genetic and pharmacogenetic research may be conducted on the DNA samples collected at baseline/Day 1 from subjects who sign an optional, additional informed consent. In particular, the impact of polymorphisms in the NOX1 and/or NOX4 genes on pharmacodynamic and therapeutic responses may be assessed.
# 4 STUDY DESIGN

This will be a double-blind, randomized, placebo-controlled, multicenter, parallel group phase 2 trial assessing a 24-week period of treatment with oral GKT137831 administered in addition to standard of care medication (UDCA) in subjects with PBC.

Subjects will be assessed for their eligibility during the screening period (Visit 1), which will last up to 4 weeks, until the baseline/Day 1 visit (Visit 2).

Eligible subjects will be randomized to oral GKT137831 (400 mg OD or 400 mg BID) or placebo, according to a 1:1:1 randomization ratio, stratified at study entry by disease severity defined as baseline serum GGT < 2.5 x the ULN or  $\geq 2.5 \text{ x}$  ULN.

Subjects will self-administer orally 400 mg OD or 400 mg BID of GKT137831 or matching placebo for a total of 24 weeks.

Baseline assessments will be performed at baseline/Day 1 (Visit 2). The 24-week treatment period will include assessments after 2 weeks of treatment (Visit 3), after 6 weeks of treatment (Visit 4), after 12 weeks of treatment (Visit 5), after 18 weeks of treatment (Visit 6) and after 24 weeks of treatment (End of Treatment/Visit 7). Subjects will be followed up for 28 days after the end of treatment (Week 28/Visit 8), totaling 6 post-baseline visits. Subjects who discontinue treatment before Week 24 will have an Early Termination visit (premature end of treatment).

Pharmacokinetic samples will be taken at Week 2, Week 12 and Week 18 (see Section 8.2.2 for the sampling time points).

Subjects will be taking a stable dose of UDCA at enrollment and will continue their UDCA treatment at a stable dose (no changes at all) during the treatment period.

A Safety Monitoring Board will oversee the conduct of the study to ensure the safety of participating subjects (see Section 9.7 for more details). An interim analysis will be conducted when 80-90% of the planned number of subjects to be randomized in the study have completed their Week 6 visit (see Section 10.3).

#### Figure 1: Study Design Flowchart

# 5 STUDY ENROLLMENT AND WITHDRAWAL

# 5.1 Population

Subjects with primary biliary cholangitis receiving a stable dose of UDCA and with persistently elevated ALP, who meet all of the inclusion criteria listed in Section 5.2 and none of the exclusion criteria listed in Section 5.3, may be included in this study. Approximately 100 subjects will be randomized.

# 5.2 Inclusion Criteria

In order to be eligible to participate in this study, a subject must meet all of the following criteria:

- 1. Male or female aged 18 to 80 years, inclusive.
- 2. Willing and able to give written informed consent and to comply with the requirements of the study.
- 3. PBC diagnosis as demonstrated by the presence of  $\geq$  2 of the following 3 diagnostic factors:
  - a) History of elevated ALP levels (>ULN) for at least 6 months
  - b) Positive AMA titer or if AMA negative or in low titer (<1:80) PBC specific antibodies (anti-GP210 and/or anti-SP100 and/or antibodies against the major M2 components [PDC-E2, 2-oxo-glutaric acid dehydrogenase complex])

  - c) Liver biopsy consistent with PBC (based on historic liver biopsy), including nonsuppurative, destructive cholangitis affecting mainly the interlobular and septal bile ducts.
- 4. Serum ALP ≥1.5 x ULN.
- 5. Serum GGT ≥1.5 x ULN.
- 6. UDCA treatment for at least 6 months and stable dose for at least 3 months prior to Visit 1.
- 7. Subjects being treated for pruritus with colestyramine must be on a stable dose of colestyramine for at least 8 weeks prior to baseline/Day 1 (Visit 2). Subjects must be willing and able to take colestyramine at least 2 hours before or after study medication.
- 8. Female subjects of childbearing potential must use a highly effective method of contraception to prevent pregnancy for 4 weeks before randomization and must agree to continue strict contraception for 90 days after last administration of IMP (see Section 5.4). Male participants with female partners of childbearing potential must be willing to use a condom and require their partner to use an additional form of adequate contraception as approved by the Investigator.

Protocol No.: GSN000300	Compound No.: GKT137831
Protocol Version No.: Final 4.0; Amendment 3	Sponsor: Genkyotex
Protocol Date: 24 July 2018	Author: Cmed Clinical Services

This requirement begins at the time of informed consent and ends 90 days after the last administration of IMP. Male study participants must also not donate sperm from baseline until 90 days after the last administration of IMP.

# 5.3 Exclusion Criteria

A potential subject who meets any of the following criteria will be excluded from participation in this study:

- 1. A positive pregnancy test or breast-feeding for female subjects.
- 2. Any hepatic decompensation, defined as a past or current history of hepatic encephalopathy, gastrointestinal tract bleeding due to esophageal varices, or ascites.
- 3. INR > 1.2 unless subject is on anticoagulant therapy.
- 4. ALT > 3 x ULN.
- 5. Total bilirubin > 1 x ULN.
- 6. Planned or current plasmapheresis or other extra-corporeal treatments (e.g., MARS) for treatment-refractory pruritus.
- History of liver transplantation, current placement on a liver transplant list or current MELD score
  ≥ 15.
- 8. Cirrhosis with complications, including history or presence of: spontaneous bacterial peritonitis, hepatocellular carcinoma.
- 9. Hepatorenal syndrome (type I or II) or Screening serum creatinine > ULN.
- 10. Competing etiology for liver disease (e.g., hepatitis C, active hepatitis B, NASH, ALD, autoimmune hepatitis, primary sclerosing cholangitis, Gilbert's Syndrome).
- 11. Subjects receiving prohibited medications within 3 months of Screening (Visit 1) according to the list (a, b and c) provided in Section 6.6.2.
- 12. Treatment with any investigational agent within 4 weeks of Screening (Visit 1) or 5 half-lives of the IMP (whichever is longer).
- 13. A history of long QT syndrome.
- 14. Evidence of any of the following cardiac conduction abnormalities during the screening period:
  - A QTc Fredericia interval > 450 milliseconds for males and > 470 milliseconds for females.
  - A second or third degree atrioventricular block not successfully treated with a pacemaker.
- 15. A history of severe cardiovascular disease defined as any of the following within the 12 weeks preceding initiation of study treatment:
  - Acute myocardial infarction or unstable angina pectoris.

- A coronary revascularization procedure.
- Congestive heart failure New York Health Association (NYHA) Class III or IV.
- Stroke, including a transient ischemic attack.
- 16. History of cancer in the preceding 5 years, except adequately treated non-melanoma skin cancer, carcinoma *in situ* of the cervix, *in situ* prostate cancer, *in situ* breast ductal carcinoma, or superficial bladder cancer stage 0).
- 17. The occurrence of any acute infection requiring systemic antibiotic therapy within 2 weeks prior to Screening (Visit 1), or HIV infection.
- 18. A history of bone marrow disorder including aplastic anemia, or marked anemia defined as hemoglobin < 10.0 g/dL (or 6.2 mmol/L).
- 19. A known hypersensitivity to GKT137831 or to any of the excipients.
- 20. Any condition which, in the opinion of the Investigator, constitutes a risk or contraindication for the participation of the subject in the study, or which could interfere with the study objectives, conduct, or evaluation.

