# 6.3.1 In case of Confirmed or Suspected Drug Induced Liver Injury

In case of any of the following events:

- Grade ≥ 2 severity liver-related AE, or
- Grade ≥ 3\_severity ALT or AST (i.e. ≥ 5x ULN), or
- Grade ≥ 2 severity total bilirubin (i.e. ≥ 1.5x ULN), or
- Grade  $\geq$  2 severity INR (i.e.  $\geq$  1.5x ULN)

The investigator will instruct the subject to interrupt IMP administration and to return to the study center within 2-3 days to perform a re-test and to undergo additional investigations (i.e. close monitoring as described in Appendix F) to assess for potential DILI. In case of confirmed or suspected DILI as assessed by the investigator, IMP administration must be permanently discontinued, in particular in the following cases:

• Re-test ALT and/or AST values ≥ 3 x baseline and greater than the ULN associated with new onset total bilirubin ≥ 2 x ULN or INR ≥ 1.5.

If subjects live in a remote area, they can be tested locally and the results communicated to the investigator site promptly.

In case of non-confirmed DILI, IMP administration will be resumed in accordance with the protocol and subject will remain under close monitoring as deemed necessary by the investigator.

Any confirmed or suspected DILI event will be closely monitored by the investigator and reported to Sponsor following the same procedure as for SAEs, as described in Section 9.5.

Withdrawals will be handled as described in Section 5.6.5.

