# 9.2 Adverse Events

# 9.2.1 Definition of Adverse Event

An AE is defined as any untoward medical occurrence in the form of signs, symptoms, abnormal laboratory findings, or disease that emerges or worsens relative to baseline during a clinical study with an IMP, regardless of causal relationship and even if no IMP has been administered.

Unchanged/stable pre-existing, chronic medical conditions present at baseline, or those medical conditions related to the underlying disease whose changes during the study that are consistent with natural disease progression are NOT considered as AEs and should not be recorded in the AE pages of the eCRF unless a worsening has occurred.

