## 9.2.1.3 Abnormal Laboratory Values/and Other Objective Measurements

Abnormal laboratory findings and other objective measurements such as vital signs and ECGs, should NOT routinely be captured and reported as AEs as they will be collected and analyzed separately in the eCRF. However, abnormal laboratory findings and other objective measurements which (i) meet the criteria for a SAE (see Section 9.3.1), or (ii) result in discontinuation of the IMP or in treatment being withheld (see Sections 5.6.4 and 6.3, respectively), or (iii) require medical intervention should be captured and reported in the AE pages of the eCRF.

If reporting an abnormal laboratory finding in the AE pages of the eCRF, a clinical diagnosis should be recorded rather than the abnormal value itself, if available (for example "anemia" rather than "decreased RBC count" or "hemoglobin = 10.5 g/dl").

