# 9.5 Drug-Induced Liver Injury

If a study subject, who has been exposed to the IMP, presents signs or symptoms of DILI, a close monitoring must be initiated and documented by the investigator. The IMP must be discontinued until re-testing is performed, additional investigations completed and a diagnosis made. If DILI is confirmed or suspected by the investigator, the investigator will complete an Expedited Liver Assessment Report form (ELAR) and submit it to Sponsor in the same timelines as a SAE (see Section 9.3.2. The ELAR form must be completed and forwarded via email or facsimile to the designated CRO safety group using the email address or fax number listed in Section 9.3.2 within 24 hours of the Investigator becoming aware of the confirmed or suspected DILI event.

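### The INR interruption trigger in Protocol 6.3.1 has no baseline term, so an eligible anticoagulated subject can be interrupted for a DILI work-up on an unchanged INR

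*Protocol*

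**What the plan says.** Exclusion 3 (Protocol 5.3, repeated in the Protocol Summary) reads "INR > 1.2 unless subject is on anticoagulant therapy". It gives no upper INR limit for the exempt subjects, and the prohibited-medication lists in 6.6.2 name no anticoagulant. Entry is otherwise restricted by exclusion 7 (MELD of 15 or more) and exclusion 20 (investigator judgement).

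Section 6.3.1 lists four findings, any one of which starts the liver-injury procedure. The INR item (Grade ≥ "2 severity INR (i.e.", followed by a cut-off of 1.5 x ULN) stands beside ALT/AST, total bilirubin and liver-related AEs. The required action is not discretionary: "The investigator will instruct the subject to interrupt IMP administration and to return to the study center within 2-3 days", for a re-test and the Appendix F investigations. Section 9.5, which covers subjects with signs or symptoms of DILI, adds: "The IMP must be discontinued until re-testing is performed, additional investigations completed and a diagnosis made".

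The way back is also stated: "In case of non-confirmed DILI, IMP administration will be resumed in accordance with the protocol". The permanent-discontinuation pattern needs re-test ALT and/or AST of at least 3 x baseline and above ULN, together with "new onset total bilirubin ≥ 2 x ULN or INR ≥ 1.5". INR is measured at every visit (8.2.1).

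**The concern.** The protocol deliberately admits subjects whose INR is raised by an anticoagulant, then applies an on-treatment rule that cannot tell that INR from a new one. If the entry value is already at or above 1.5 x ULN, the rule is met at the first on-treatment visit without any change, and can be met again at later visits. The subject loses dosing days and undergoes a DILI work-up that reflects the anticoagulant rather than study drug.

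A related wording gap is Appendix F item 10, which suggests considering intravenous vitamin K when INR is also raised. It has no caveat for a subject whose INR is raised on purpose.

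**Working it through.** There is no stated figure to reproduce. The check compares entry limits with triggers, then sizes the consequence.

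**1. Entry limit against trigger**

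| Measure | Entry limit (5.3) | Trigger (6.3.1) | Margin at entry |
|---|---|---|---|
| ALT | 3 x ULN | 5 x ULN | yes |
| Total bilirubin | 1 x ULN | 1.5 x ULN | yes |
| INR, no anticoagulant | 1.2 | 1.5 x ULN | yes (step 2) |
| INR, on anticoagulant | none | 1.5 x ULN | not assured |

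AST has no entry limit of its own, so it is left out. INR is the only trigger measure with a written entry exemption.

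**2. Trigger level.** The documents give no ULN for INR. For an assumed ULN of 1.0, 1.1, 1.2 or 1.3, the trigger is 1.5 x ULN = 1.50, 1.65, 1.80 or 1.95. A non-anticoagulated entrant has INR of at most 1.2, which is below all four. Only the exemption opens the gap.

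**3. Does MELD < 15 close the gap?** The documents give no MELD formula. As an illustration only, assume the classic form, MELD = 3.78 ln(bilirubin) + 11.2 ln(INR) + 9.57 ln(creatinine) + 6.43. Take bilirubin *b* and creatinine *c* at 1.0-1.2 mg/dL, since exclusions 5 and 9 hold both at or below ULN. Solving for MELD = 15:

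INR = exp[(15 − 6.43 − 3.78 ln *b* − 9.57 ln *c*) / 11.2]

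- *b* = 1.0, *c* = 1.0: exp(8.57/11.2) = 2.15
- *b* = 1.2, *c* = 1.0: 2.02
- *b* = 1.0, *c* = 1.2: 1.84
- *b* = 1.2, *c* = 1.2: 1.73

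Against these ceilings, triggers of 1.50 and 1.65 leave an eligible band in all four cases. A trigger of 1.80 leaves one in three cases, and 1.95 in two. Rounding the score (cut at 14.5) lowers the ceilings to 1.65-2.06 and narrows the band further. MELD therefore shrinks the group but does not remove it over most of the assumed range.

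**4. Does baseline enter the trigger elsewhere?** In 6.3.1 a comparison with baseline is attached to ALT/AST, and new onset to bilirubin, but only in the permanent-discontinuation pattern. Appendix F item 3 refers to baseline for when monitoring can ease, not for starting the procedure. The interruption trigger itself has no such term.

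**5. Dosing time lost.** Treatment lasts 24 x 7 = 168 days. Time to re-test is 24-72 hours (Appendix F item 2) or 2-3 days (6.3.1), so about 1-3 days.

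- One cycle: 1/168 = 0.6% to 3/168 = 1.8%.
- Recurrence at every visit with dosing still to follow (Weeks 2, 6, 12, 18): 4 x 1 = 4 days (2.4%) to 4 x 3 = 12 days (7.1%).

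These figures run to the re-test only; investigations under 9.5 could extend them. Falling below the 80% compliance limit in 6.5 on this account alone would need more than 0.20 x 168 = 33.6 lost days, or 8.4 days in each of four cycles.

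**6. Candidate limits**

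| Baseline INR | ULN (assumed) | Now: 1.5 x ULN | 1.5 x baseline | Greater of the two |
|---|---|---|---|---|
| 1.0 | 1.2 | 1.80 | 1.50 | 1.80 |
| 1.8 | 1.2 | 1.80 | 2.70 | 2.70 |

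Using 1.5 x baseline alone would be stricter than the present rule for a near-normal baseline whenever ULN exceeds 1.0. Taking the greater value avoids that.

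**The case against.** **The trigger is a grade, not a bare number.** The protocol grades AEs by CTCAE v4, and that INR row might carry a baseline or anticoagulant form. The row is not reproduced, so the documents cannot settle this. What they do print is an explanatory cut-off of 1.5 x ULN, and a site will apply that.

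**An AE must be a change.** Section 9.2.1 defines an AE as something that "emerges or worsens relative to baseline during a clinical study with an IMP". This does not govern the trigger, because 6.3.1 lists the laboratory values separately from liver-related AEs and any one is enough.

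**The definition does weaken a reporting claim.** A reader might infer that the unchanged INR will appear among TEAEs leading to study drug interruption. Section 9.2.1.3 gives some ground for this, since it asks for laboratory findings that "result in discontinuation of the IMP or in treatment being withheld" to be recorded as AEs. But 9.2.1 says stable pre-existing conditions are not AEs, and SAP 8.10.1 limits TEAEs to events that start on or after first dose, or earlier ones that increase in severity or relationship (an undatable AE counts by default). The texts pull in different directions, so entry into that table is not shown.

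**Interrupt-and-re-test is a defensible caution.** The dose is higher and treatment longer than studied before, and section 2.3 expects drug to accumulate in the liver. This stands as a reason to keep the other triggers intact and to go on re-testing INR rises in anticoagulated subjects. It does not justify repeated work-ups of a value that has not moved.

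**The group is rare and the loss slight.** This stands, and sets the size of the point.

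**Conclusion.** The point holds as a minor one. As printed, 6.3.1 requires interruption and a DILI work-up on an unchanged INR for any eligible anticoagulated subject who entered at or above 1.5 x ULN. That rests on the text alone; the ULN range and the MELD formula only indicate how wide the eligible band might be. The documents give no figure for anticoagulant use or entry INR, so the number affected is unknown and probably small.

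Two further readings are tempting and not supported. One is that these subjects would be permanently withdrawn. Drug resumes if the investigator neither confirms nor suspects DILI, the stated discontinuation pattern also needs the ALT/AST rise, and the mandatory-stop list in Appendix F has no INR criterion. The other is that efficacy is at risk. No endpoint, power or alpha figure changes, and the loss to re-test is at most 12 of 168 days under the recurrence assumption.

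**What to change.** In 6.3.1 add: *For subjects on anticoagulant therapy at baseline, the isolated INR trigger is INR ≥ the greater of 1.5 x ULN and 1.5 x baseline; a rise that coincides with an anticoagulant dose change is re-tested, not disregarded.* Baseline can follow SAP 6.5 (last value on or before first dose). Leave the ALT/AST, bilirubin and liver-AE triggers and the permanent-discontinuation pattern as they are.

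In Appendix F item 10 add that the vitamin K trial does not apply where the INR is raised by anticoagulant therapy.

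The cost is one sentence and one short caveat, with no new assessments. The downside is slightly lower INR sensitivity in anticoagulated subjects with a raised baseline: at a baseline of 1.8 the isolated trigger becomes 1.5 x 1.8 = 2.7. The other liver triggers still apply to them in full.
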